		above baseline	<2.0 x above baseline	above baseline
Creatinine	NA	<90 to 60 ml/min or	<60 to 30ml/min or	<30 ml/min or
Clearance  or		ml/min/1.73 m  OR 10	ml/min/1.73 m  OR	ml/min/1.73 m  OR
eGFR, Low		to <30% decrease from	$\geq$ 30 to <50% decrease	$\geq$ 50% decrease from
Report only one		baseline	from baseline	baseline or dialysis needed
Glucose	110 to 125	>125 to 250	>250 to 500	>500
(mg/dL; mmol/L )	6.11 to <6.95	6.95 to <13.89	13.89 to <27.75	≥27.75
Fasting, High	0.11 10 \0.95	0.95 10 (15.09	15.07 10 -27.75	- 27.75
Nonfasting, High	116 to 160	>160 to 250	>250 to 500	>500
11011justing, 11151	6.44 to <8.89	8.89 to <13.89	13.89 to <27.75	≥27.75
Glucose, Low	55 to 64	40 to <55	30 to <40	<30
(mg/dL; mmol/L )	3.05 to 3.55	2.22  to  < 3.05	1.67 to <2.22	<1.67
$\geq 1$ month of age				
<1 month of age	50 to 54	40 to < 50	30 to <40	< 30
	2.78 to 3.00	2.22 to <2.78	1.67 to <2.22	<1.67
Lactate, High	ULN to <2.0 x ULN	$\geq 2.0 \text{ x ULN without}$	Increased lactate with	Increased lactate with
, ,	without acidosis	acidosis	pH <7.3 without life-	pH <7.3 with life-
			threatening	threatening
			consequences	consequences
Lipase, High	1.1 to <1.5 x ULN	1.5 to <3.0 x ULN	3.0 to <5.0 x ULN	≥5.0 x ULN
Lipid Disorders				
(mg/dL; mmol/L )				
Cholesterol,	200 to <240	240 to <300	≥300	NA
Fasting, High	5.18 to <6.19	6.19 to <7.77	≥7.77	
$\geq 18$ years of age	1=0			
<18 years of age	170 to <200	200 to <300	≥300	NA
	4.40 to <5.15	5.15 to <7.77	≥7.77	274
LDL, Fasting, High	130  to  < 160	160  to  <190	$\geq 190$	NA
$\geq 18$ years of age	3.37 to <4.12 110 to <130	4.12 to <4.90 130 to <190	$\geq 4.90$	NTA
>2 to <18 years of	2.85  to  <3.34	3.34 to <4.90	≥190 ≥4.90	NA
age Triglycerides,	2.85  to  < 3.34 150 to 300	3.34 to <4.90 >300 to 500	$\geq 4.90$ >500 to <1,000	>1,000
Fasting, High	1.71 to 3.42	>3.42 to 5.7	>5.7 to 11.4	>11.4
Magnesium  , Low	1.71 to 3.42	0.9 to <1.2	0.6 to <0.9	<0.6
(mEq/L; mmol/L )	0.60  to  < 0.70	0.9  to  < 1.2 0.45 to < 0.60	0.30  to  < 0.45	<0.0
Phosphate, Low	2.0  to < LLN	1.4  to < 2.0	1.0 to <1.4	<1.0
(mg/dL; mmol/L )	0.81  to < LLN	$0.65 \ to < 0.81$	0.32  to  < 0.65	<0.32
>14 years of age				··
1 to 14 years of age	3.0 to <3.5	2.5 to <3.0	1.5 to <2.5	<1.5
J - J - G-	0.97 to <1.13	0.81 to <0.97	0.48  to  < 0.81	<0.48
<1 year of age	3.5 to <4.5	2.5 to <3.5	1.5 to <2.5	<1.5
	1.13 to <1.45	0.81 to <1.13	0.48 to <0.81	<0.48
Potassium, High	5.6 to <6.0	6.0 to <6.5	6.5 to <7.0	≥7.0
(mEq/L; mmol/L)	5.6 to <6.0	6.0 to <6.5	6.5 to <7.0	≥7.0
Potassium, Low	3.0 to <3.4	2.5 to <3.0	2.0 to <2.5	<2.0
(mEq/L; mmol/L )	3.0  to  < 3.4	2.5 to <3.0	2.0  to  < 2.5	<2.0

 $\frac{(1126)}{15}$  Use the applicable formula (i.e., Cockroft-Gault in mL/min or Schwatrz in mL/min/1.73m^2).  To convert a magnesium value from mg/dL to mmol/L, laboratories should multiply by 0.4114.

## D/C/F/TAF (darunavir/cobicistat/emtricitabine/tenofovir alafenamide) Clinical Protocol TMC114IFD3013 Amendment 4

PARAMETER	GRADE 1 MILD	GRADE 2 MODERATE	GRADE 3 SEVERE	GRADE 4 POTENTIALLY LIFE- THREATENING
Sodium, High	146 to <150	150 to <154	154 to <160	≥160
(mEq/L; mmol/L)	146 to <150	150 to <154	154 to <160	≥160
Sodium, Low	130 to <135	125 to <130	121 to <125	≤120
(mEq/L; mmol/L)	130 to <135	125 to <135	121 to <125	≤120
Uric Acid, High	7.5 to <10.0	10.0 to <12.0	12.0 to <15.0	≥15.0
(mg/dL; mmol/L)	0.45 to <0.59	0.59 to <0.71	0.71 to <0.89	$\geq 0.89$

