## 9.4. Safety Evaluations

The study will include the following evaluations of safety and tolerability according to the time points specified in the Time and Events Schedule: AE reporting, clinical laboratory tests (including biochemistry, hematology, urinalysis, urine chemistry, and renal biomarkers), vital signs, physical examinations (complete or symptom-directed), and bone biomarkers and DXA scans of spine and hip (only for subjects participating in the substudy). These protocol

procedures are described in Sections 9.4.1 through 9.4.5. In addition to these measurements, guidelines for the management of toxicities are described in Section 9.5.

Any clinically relevant abnormalities occurring at screening (from signing the ICF) and any clinically relevant changes occurring during the study must be recorded in the AE section of the eCRF.

Clinical events and clinically significant laboratory abnormalities will be graded according to the Division of AIDS (DAIDS) grading table (see Attachment 2).

Any evaluations showing abnormal results at any time during the study will be followed until satisfactory clinical resolution or stabilization. All grade 3 and grade 4 laboratory abnormalities and laboratory abnormalities resulting in an increase of 2 DAIDS grades from baseline will be followed until return to baseline or within 1 grade from baseline (ie,  $\leq$  grade 2) (for further details, see Section 9.5.1).

Any evaluations at the ESTD visit showing abnormal results indicating that there is a possible causal relationship with study drug, need to followed by the investigator (as often as deemed prudent) until satisfactory clinical resolution or stabilization. Certain long-term AEs of ARV therapy cannot be followed to resolution within the setting of this protocol; in these cases follow-up will be the responsibility of the treating physician, which will be agreed upon with the sponsor's medical monitor.

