# 9.4.2. Clinical Laboratory Tests

Blood samples for biochemistry, hematology and serum pregnancy testing (females only, at screening only or if urine pregnancy test is positive), and a urine sample for urinalysis by dipstick, urine chemistry, renal biomarkers, and urine pregnancy testing (except at screening) will be collected at the time points specified in the Time and Events Schedule.

For laboratory assessments that need to be performed fasted while the subject has not fasted prior to the visit, the visit may proceed, but the subject must return within 72 hours in a fasted state to provide the necessary sample(s) for the assessments.

All clinical laboratory testing will be performed by the central laboratory and results will be sent to the investigator. The investigator must review the laboratory report, document this review, and

record any clinically relevant findings at screening and changes occurring during the study in the AE section of the eCRF (see also Section 12.2). The laboratory reports must be filed with the source documents.

The central laboratory will send the investigator and the sponsor an alert form whenever a grade 3 or 4 laboratory abnormality (see Attachment 2) has been observed. In case a grade 3 or grade 4 laboratory abnormality occurs, a confirmatory test should be performed preferably within 72 hours after the results have become available, before study medication interruption or discontinuation unless such delay is not consistent with good medical practice.

If a grade 3 or 4 laboratory abnormality is well documented prior to the start of the study and is not considered a safety concern by investigator, a confirmatory retest is not mandatory. The following laboratory abnormalities do not warrant mandatory confirmation:

- Asymptomatic grade 3 or grade 4 glucose elevations in subjects with pre-existing diabetes;
- Asymptomatic grade 3 or grade 4 triglyceride or cholesterol elevations.

For further details on the management of grade 3 or 4 laboratory toxicities, see Section 9.5.1 and Attachment 4.

The following tests will be performed by the central laboratory:

- Urine chemistry panel: creatinine, sodium, phosphate, glucose, protein, albumin; (quantitative measurement).
- Urinalysis by dipstick: specific gravity, pH, glucose, protein, blood, ketones, bilirubin, urobilinogen, nitrite, and leukocyte esterase.

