#### **Clinical Laboratory Tests**

Laboratory data will be summarized by treatment arm and type of test. Descriptive statistics will be calculated for each laboratory analyte for observed values and changes from baseline at each scheduled time point. Graphical presentation of changes in laboratory parameters can be made as applicable. Abnormalities will be determined according to the DAIDS grading table (see Attachment 2) and in accordance with the normal ranges of the clinical laboratory. Maximum toxicity grade after baseline will be tabulated and special attention will be given to the subjects who develop grade 3 or 4 toxicities.

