## Attachment 2: Division of AIDS Table for Grading the Severity of Adult and Pediatric Adverse Events

The Division of AIDS Table for Grading the Severity of Adult and Pediatric Adverse Events (version 2.0, November 2014), or 'DAIDS grading table', is a descriptive terminology to be utilized for AE reporting in this study. A grading (severity) scale is provided for each AE term.

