#### Determining Severity Grade

If the severity of an AE could fall under either 1 of 2 grades (eg, the severity of an AE could be either grade 2 or grade 3), select the higher of the 2 grades for the AE.

Laboratory normal ranges should be taken into consideration to assign gradings to a laboratory value.

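### Adult low-phosphate grading limits in Attachment 2 are different concentrations in mg/dL and mmol/L, and no scale is named as governing

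*Protocol*

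**What the plan says.** All subjects are at least 18 (Protocol 4.1), so the row for ages over 14 in the Chemistries part of Attachment 2 applies. Its mg/dL line reads "Phosphate, Low 2.0 to < LLN 1.4 to < 2.0 1.0 to <1.4 <1.0". The mmol/L line below it has 0.81 up to the lower limit of normal (LLN) for grade 1, 0.65 to below 0.81 for grade 2, 0.32 to below 0.65 for grade 3, and below 0.32 for grade 4. The table reproduces an external one, the DAIDS grading table, version 2.0 of November 2014.

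Protocol 11.6 grades laboratory abnormalities by this table and "in accordance with the normal ranges of the clinical laboratory". SAP 5.5.1 sends the reader back to the protocol. Neither names a unit for phosphate.

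The grades are used in several places:

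- Protocol 9.4.2: "The central laboratory will send the investigator and the sponsor an alert form whenever a grade 3 or 4 laboratory abnormality" is seen, and a confirmatory test should follow.
- Protocol 9.5.1: drug is withheld for a confirmed, clinically relevant grade 3 result judged related to it.
- Protocol 11.6: "Maximum toxicity grade after baseline will be tabulated".
- SAP 5.5.2: cross-tabulations of worst grade against reference.
- SAP 5.5.3.2: a confirmed rise of at least one grade in hypophosphatemia is one of four tubulopathy markers.

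**The concern.** Two lines that should express the same limits in two units do not. Because the documents do not say which line governs, the same serum phosphate can be given two different grades, and a reader of the SAP cannot reproduce the grading.

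At the grade 2/3 limit the difference has consequences for the subject: the alert and retest under 9.4.2 and, if the result is confirmed, clinically relevant and judged related, withholding of drug under 9.5.1. For the analysis, it carries into the maximum-grade and cross-tabulated toxicity tables and into the phosphate marker of proximal tubulopathy. Renal safety is a main question in a trial that replaces TDF with TAF.

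**Working it through.** **Inputs.** The printed limits come from the low-phosphate rows of Attachment 2. The conversion is mmol/L = mg/dL × 10/30.974 = mg/dL × 0.3229, with phosphate expressed as phosphorus. The table's own paediatric rows give the same factor, so the check does not depend on an outside constant.

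| Row | mg/dL printed | mmol/L printed | Ratio | mg/dL × 0.3229 |
|---|---|---|---|---|
| Under 1 year | 4.5 | 1.45 | 0.322 | 1.453 |
| 1 to 14 years | 3.5 | 1.13 | 0.323 | 1.130 |
| 1 to 14 years | 3.0 | 0.97 | 0.323 | 0.969 |
| 1 to 14 years | 2.5 | 0.81 | 0.324 | 0.807 |
| 1 to 14 years | 1.5 | 0.48 | 0.320 | 0.484 |
| Adult, grade 1/2 | 2.0 | 0.81 | **0.405** | **0.646** |
| Adult, grade 2/3 | 1.4 | 0.65 | **0.464** | **0.452** |
| Adult, grade 3/4 | 1.0 | 0.32 | 0.320 | 0.323 |

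The paediatric pairs and the adult 3/4 limit reproduce with ratios of 0.320 to 0.324. The adult 1/2 and 2/3 limits do not. In reverse, 0.81/0.3229 = 2.51 mg/dL, 0.65/0.3229 = 2.01 and 0.32/0.3229 = 0.99. The table thus pairs 0.81 mmol/L with 2.5 mg/dL for children and with 2.0 mg/dL for adults.

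**Effect on grades.**

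| Serum phosphate, mg/dL | mg/dL line | mmol/L line |
|---|---|---|
| 2.0 to <2.5, and below LLN | grade 1 | grade 2 |
| 1.4 to <2.0 | grade 2 | grade 3 |
| 1.0 to <1.4 | grade 3 | grade 3 |
| <1.0 | grade 4 | grade 4 |

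**How many reportable values differ.** The documents give no LLN, so I assume 2.2 to 2.7 mg/dL, leave values at or above LLN ungraded, and round mmol/L to two decimals. In steps of 0.1 mg/dL:

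- LLN 2.2: 8 values are graded differently (1.4 to 2.1).
- LLN 2.5 and LLN 2.7: 11 values (1.4 to 2.4).
- Grade 3 alert: 6 values differ (1.4 to 1.9) at every LLN in the range.

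Without rounding, the counts are 8, 11 and 12 at LLN 2.2, 2.5 and 2.7, and 7 for the alert, because 2.0 mg/dL is 0.646 mmol/L and so below 0.65.

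**SAP marker (rise of at least one grade from reference).** If the reference is at or above LLN it is ungraded on both lines, and any later value below LLN is at least grade 1 on both, so the marker cannot differ. It can differ when the reference is already graded. At LLN 2.5, a fall from 1.5 to 1.3 mg/dL is grade 2 to 3 by mg/dL (marker met) and grade 3 to 3 by mmol/L (not met).

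**The case against.** The mismatch itself is hard to dispute. An extraction fault is unlikely, because each adult line runs continuously from grade to grade and the mmol/L values convert cleanly to 2.5, 2.0 and 1.0 mg/dL. The case on the other side is about weight.

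- **The table is external, and mg/dL is implied.** The row lists mg/dL first, and the SAP's lipid, creatinine and glucose thresholds are in mg/dL. This suggests a scale without specifying one, and Protocol 9.5.7 and 9.5.8 print mmol/L first. The trial adopts the table as its working rule whatever its origin.
- **A tie-break exists.** Attachment 2 tells the grader to "select the higher of the 2 grades for the AE", which would favour the mmol/L line. That instruction concerns adverse-event severity, and Protocol 12.2 says laboratory abnormalities are usually not recorded as adverse events. The point stays open.
- **Little would change.** This largely stands. One central laboratory does the testing and local results are excluded, so one scale was probably applied throughout. The Week 96 analysis tests no formal hypothesis. Follow-up does not hinge on the unit either: "Any evaluations showing abnormal results at any time during the study will be followed until satisfactory clinical resolution or stabilization". Only the grade at which follow-up may stop would differ.
- **The counts are of values, not subjects.** True; the documents give no frequency of low phosphate.
- **The marker result depends on leaving values at or above LLN ungraded.** Correct. If the printed mmol/L bands were applied literally with LLN 2.3, a fall from 2.4 to 2.1 mg/dL would be grade 0 to 1 by mg/dL but 2 to 2 by mmol/L. However, 11.6 and Attachment 2 ("Laboratory normal ranges should be taken into consideration to assign gradings to a laboratory value") support the assumption.
- **Tubulopathy may not require creatinine.** SAP 5.5.3.2 speaks of any two of four parameters and then, in parentheses, of creatinine plus another. On the parenthetical reading, phosphate alone with a non-creatinine marker does not qualify.

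**Conclusion.** The concern holds. Two of the three adult low-phosphate limits are different concentrations in the two units, and the documents name no governing scale. They also cannot show which line is wrong. The difference is one grade for 1.4 to below 2.0 mg/dL (grade 2 or 3) and one grade for 2.0 to below 2.5 mg/dL when under LLN (grade 1 or 2). The first band moves the alert and drug-withholding threshold. These bands follow from the printed limits, to rounding at 2.0 mg/dL; the counts of 8 to 11 values also rest on the assumed LLN range and rounding.

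It is a minor safety-grading correction. The primary endpoint and descriptive summaries of phosphate are untouched, and one consistently applied scale is likely. Consistent use would not, however, show that the intended scale was used.

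**What to change.** 1. Check the adult row against the cited grading table and correct one line. Either keep 2.0/1.4/1.0 mg/dL with 0.65/0.45/0.32 mmol/L, or keep 0.81/0.65/0.32 mmol/L with 2.5/2.0/1.0 mg/dL. If the source carries the same mismatch, the sponsor should choose a scale and record the choice.
2. Add a sentence to SAP 5.5.1 naming the governing phosphate scale.
3. Confirm which scale the central laboratory's grading program used.
4. While there, proofread the rest of the reproduced table. Low sodium grade 2 is printed as 125 to <130 mEq/L but 125 to <135 mmol/L.

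The cost is a table correction, a SAP sentence and a query to the laboratory. If the program already uses the right scale, nothing is regraded. If not, phosphate grades are re-derived from existing results. SAP section 5 repeats the comparative phase in the Week 96 tables, so these could then differ from the Week 24 and Week 48 tables already produced, and a note should explain why. No new data are needed.

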#### D/C/F/TAF (darunavir/cobicistat/emtricitabine/tenofovir alafenamide)

## NCT02269917

Clinical Protocol TMC114IFD3013 Amendment 4

	HEMATOLOGY				
PARAMETER	GRADE 1 MILD	GRADE 2 MODERATE	GRADE 3 SEVERE	GRADE 4 POTENTIALLY LIFE- THREATENING	
Absolute CD4+				THREATENING	
Count, Low					
(cell/mm  ; cells/L )	300 to <400	200 to <300	100 to <200	<100	
>5 years of age	300 to <400	200 to <300	100 to <200	<100	
(not HIV infected)					
Absolute Lymphocyte					
Count, Low					
(cell/mm  ; cells/L )	600  to  < 650	500 to <600	350 to <500	<350	
>5 years of age	$0.600 \times 10^9$ to < 0.650	$0.500 \times 10^9$ to < 0.600	$0.350 \times 10^9$ to < 0.500 x	$<0.350 \times 10^9$	
(not HIV infected)	$x 10^9$	$x 10^9$	109		
Absolute Neutrophil					
Count (ANC), Low (cells/mm  ; cells/L )	800 to 1,000	600 to 799	400 to 599	<400	
$(cells/mm^2; cells/L)$ >7 days of age	0.800  to  1,000 $0.800 \text{ x } 10^9 \text{ to } 1.000 \text{ x}$	0.600  to  799 $0.600 \times 10^9 \text{ to } 0.799 \text{ x}$	0.400  to  599 $0.400 \times 10^9 \text{ to } 0.599 \text{ x}$	<400 $<0.400 \times 10^{9}$	
/ aays of age	$10^{9}$	$10^{9}$	$10^{9}$	$\sim 0.400 \ x \ 10$	
2 to 7 days of age	1,250 to 1,500	1,000 to 1,249	750 to 999	<750	
2 10 7 uuys 0j uge	1,250  to  1,500 $1.250 \text{ x } 10^9 \text{ to } 1.500 \text{ x}$	1,000  to  1,249 $1.000 \times 10^9 \text{ to } 1.249 \text{ x}$	$0.750 \times 10^9$ to $0.999 \times 10^{-10}$	$< 0.750 \times 10^9$	
	$1.250 \times 10^{-10} 1.500 \times 10^{9}$	$1.000 \times 10^{-10} 1.249 \times 10^{9}$	$10^9$	<0.750 x 10	
≤l day of age	4,000 to 5,000	3,000 to 3,999	1,500 to 2,999	<1,500	
_1 day of age	$4.000 \times 10^9$ to $5.000 \times 10^9$	$3.000 \times 10^9$ to $3.999 \times 10^9$	$1.500 \times 10^9$ to 2.999 x	$< 1.500 \times 10^9$	
	$10^9$	$10^9$	$10^9$	11000 10	
Fibrinogen,	100 to <200	75 to <100	50 to <75	<50	
Decreased (mg/dL;	1.00 to <2.00	0.75 to <1.00	0.50  to  < 0.75	< 0.50	
g/L)	OR	OR	OR	OR	
	0.75 to <1.00 x LLN	≥0.50 to <0.75 x LLN	0.25 to <0.50 x LLN	<0.25 x LLN	
				OR Associated with	
15				gross bleeding	
Hemoglobin  , Low					
$(g/dL; mmol/L)^{18}$					
$\geq 13$ years of age	10.0 to 10.9	9.0 to <10.0	7.0 to <9.0	<7.0	
(male only)	6.19 to 6.76	5.57 to <6.19	4.34 to <5.57	<4.34	
$\geq 13$ years of age	9.5 to 10.4	8.5 to <9.5	6.5 to <8.5	<6.5	
(female only)	5.88 to 6.48	5.25  to  < 5.88	4.03  to  < 5.25	<4.03	
57 days of age to <13 years of age	9.5 to 10.4 5.88 to 6.48	8.5 to <9.5 5.25 to <5.88	6.5 to <8.5 4.03 to <5.25	<6.5 <4.03	
<15 years of age (male and female)	5.00 10 0.40	5.25 10 ~5.00	4.05 10 ~ 5.25	~4.03	
(male and female) 36 to 56 days of	8.5 to 9.6	7.0 to <8.5	6.0 to <7.0	<6.0	
age (male and	5.26 to 5.99	4.32 to <5.26	3.72  to  <4.32	<3.72	
female)	5.20 10 5.99	1.52 10 3.20	5.72 10 41.52	-5.72	
22 to 35 days of	9.5 to 11.0	8.0 to <9.5	6.7 to <8.0	<6.7	
age (male and	5.88 to 6.86	4.94  to  < 5.88	4.15 to <4.94	<4.15	
female)					
8 to $\leq 21$ days of	11.0 to 13.0	9.0 to <11.0	8.0 to <9.0	<8.0	
age (male and	6.81 to 8.10	5.57 to <6.81	4.96 to <5.57	<4.96	
female)					
$\leq$ 7 days of age	13.0 to 14.0	10.0 to <13.0	9.0 to <10.0	<9.0	
(male and female)	8.05 to 8.72	6.19 to <8.05	5.59 to <6.19	<5.59	
INR, High	1.1 to <1.5 x ULN	1.5 to <2.0 x ULN	2.0 to <3.0 x ULN	$\geq$ 3.0 x ULN	
(not on anticoagulation					
therapy)					
Methemoglobin (%	5.0 to <10.0%	10.0 to <15.0%	15.0 to <20.0%	≥20.0%	
hemoglobin)	lefined as sex at birth.				

 Male and female sex are defined as sex at birth.  The conversion factor used to convert g/dL to mmol/L is 0.6206 and is the most commonly used conversion factor. For grading hemoglobin results obtained by an analytic method with a conversion factor other than 0.6206, the result must be converted to g/dL using the appropriate conversion factor for the particular laboratory.

# D/C/F/TAF (darunavir/cobicistat/emtricitabine/tenofovir alafenamide) \_\_\_\_\_Clinical Protocol TMC114IFD3013 Amendment 4

PARAMETER	GRADE 1 MILD	GRADE 2 MODERATE	GRADE 3 SEVERE	GRADE 4 POTENTIALLY LIFE- THREATENING
PTT, High (not on anticoagulation therapy)	1.1 to <1.66 x ULN	1.66 to <2.33 x ULN	2.33 to <3.00 x ULN	≥3.00 x ULN
Platelets, Decreased (cells/mm  ; cells/L )	100,000 to $<124,999$ 100.000 x 10  to $<124.999 x 10^9$	50,000  to  <100,000 $50.000 x 10^9 \text{ to}$ $<100.000 x 10^9$	25,000 to $<$ 50,000 25.000 x 10  to <50.000 x 10 	<25,000 <25.000 x 10 
PT, High (not on anticoagulation therapy	1.1 to <1.25 x ULN	1.25 to <1.50 x ULN	1.50 to <3.00 x ULN	≥3.00 x ULN
WBC, Decreased (cells/mm  ; cells/L) >7 days of age ≤7 days of age	2,000 to 2,499 2.000 x 10  to 2.499 x 10  5,500 to 6,999 5.500 x 10  to 6.999 x 10 	1,500 to 1,999 $1.500 \times 10^9$ to 1.999 x $10^9$ 4,000 to 5,499 $4.000 \times 10^9$ to 5.499 x $10^9$	1,000 to 1,499 $1.000 \times 10^9$ to 1.499 x $10^9$ 2,500 to 3,999 $2.500 \times 10^9$ to 3.999 x $10^9$	<1,000 <1.000 x 10  <2,500 <2.500 x 10 

URINALYSIS					
PARAMETER	GRADE 1 MILD	GRADE 2 MODERATE	GRADE 3 SEVERE	GRADE 4 POTENTIALLY LIFE- THREATENING	
Glycosuria (random collection tested by dipstick)	Trace to 1+ or ≤250 mg	2+ or >250 to ≤500 mg	>2+ or >500 mg	NA	
Hematuria (not to be reported based on dipstick findings or on blood believed to be of menstrual origin)	6 to <10 RBCs per high power field	≥10 RBCs per high power field	Gross, with or without clots OR With RBC casts OR Intervention indicated	Life-threatening consequences	
Proteinuria (random collection tested by dipstick)	1+	2+	3+ or higher	NA	

#### APPENDIX A: TOTAL BILIRUBIN TABLE FOR TERM AND PRETERM NEONATES

PARAMETER	GRADE 1	GRADE 2	GRADE 3	GRADE 4
	MILD	MODERATE	SEVERE	POTENTIALLY
				LIFE-
				THREATENING
Total Bilirubin  ,				
High (mg/dL;				
$\mu mol/L)^{20}$				
Term Neonate 				
<24 hours of age	4 to <7	7 to <10	10 to <17	≥17
	68.4 to <119.7	119.7 to <171	171 to <290.7	≥290.7
24 to <48 hours of	5 to <8	8 to <12	12 to <19	≥19
age	85.5 to <136.8	136.8 to <205.2	205.2 to <324.9	≥324.9
48 to <72 hours of	8.5 to <13	13 to <15	15 to <22	≥22
age	145.35 to <222.3	222.3 to <256.5	256.5 to <376.2	≥376.2
72 hours to	11 to <16	16 to <18	18 to <24	≥24
<7 days of age	188.1 to <273.6	273.6 to <307.8	307.8 to <410.4	≥410.4
7 to 28 days of age	5 to <10	10 to <20	20 to <25	≥25
(breast feeding)	85.5 to <171	171 to <342	342 to <427.5	≥427.5
7 to 28 days of age	1.1 to <1.6 x ULN	1.6 to <2.6 x ULN	2.6 to <5.0 x ULN	$\geq$ 5.0 x ULN
(not breast				
feeding)				
Preterm Neonate 				
35 to <37 weeks	Same as for Total	Same as for Total	Same as for Total	Same as for Total
gestational age	Bilirubin, High, Term	Bilirubin, High, Term	Bilirubin, High, Term	Bilirubin, High, Term
	Neonate (based on	Neonate (based on	Neonate (based on	Neonate (based on
	days of age).	days of age).	days of age).	days of age).
32 to <35 weeks	NA	NA	10 to <14	≥14
gestational age			171 to <239.4	≥239.4
and $<7$ days of age				
28 to <32 weeks	NA	NA	6 to <10	≥10
gestational age			102.6 to <171	≥171
and $<7$ days of age				
<28 weeks	NA	NA	5 to <8	$\geq 8$
gestational age			85.5 to <136.8	≥136.8
and $<7$ days of age				
7 to 28 days of age	5 to <10	10 to <20	20 to <25	≥25
(breast feeding)	85.5 to <171	171 to <342	342 to <427.5	≥427.5
7 to 28 days of age	1.1 to <1.6 x ULN	1.6 to <2.6 x ULN	2.6 to <5.0 x ULN	$\geq$ 5.0 x ULN
(not breast				
feeding)		ex because of rapidly changin		

 Severity grading for total bilirubin in neonates is complex because of rapidly changing total bilirubin normal ranges in the first week of life followed by the benign phenomenon of breast milk jaundice after the first week of life. Severity grading in this appendix corresponds approximately to cut-offs for indications for phototherapy at grade 3 and for exchange transfusion at grade 4.  A laboratory value of 1 mg/dL is equivalent to 17.1  $\mu$ mol/L.  Definitions: Term is defined as  $\geq$ 37 weeks gestational age; near-term, as  $\geq$ 35 weeks gestational age; preterm, as <35 weeks gestational age; and

neonate, as 0 to 28 days of age.

